### Visits 5 and 6 - 6 and 12 months (tasks for the recruiting physician)

- Physician/ nurse: Interview the patient on the effect of the medication by filling out the adrenal insufficiency form in Noklus Diabetes. Review dosing/ compliance, extra doses, side-effects, use of self-injection, and adrenal crises management.
- Regular blood chemistry including hemoglobin, Erythrocyte volume fraction, leucocytes, thrombocytes, creatinine, Na, K, calcium, magnesium, alanine amino transferase.
- Biobanking: serum and EDTA, urine, saliva (0,1 and 4 hours after morning dose), and hair examples.
- Patient: PROMS, including HRQoL questionnaires. At visit 5 or 6: Sleep diary actipragphy and sleep radar.

© 2015-2021 TransCelerate BioPharma

Doc. No. CT 2.01.01. Valid from 31 Jan 2022. Only the electronic version is valid.

Page 32 of 65

• At visit 6: Bone mineral density measurement, body composition, and measure bone markers as well as vitamin D.

# 8.2. Efficacy Assessments

Planned timepoints for all assessments are provided in the SoA.

### **8.2.1.** Patient Reported Outcome (PROMs)

- Two HRQoL will be sampled at baseline and after 1, 6 and 12 months; the generic questionnaire RAND-36 and the PAI-specific questionnaire AddiQoL. RAND-36 is thoroughly validated and extensively used and suitable both for comparison of HRQoL scores between PAI and healthy controls, and for comparing score between PAI and other disease groups (20). The AddiQoL is developed and thoroughly validated by us as a PAI-specific HRQoL instrument, more sensitive for detecting changes in HRQoL over time in PAI (21).
- For evaluation of sleep, Sleep Diary will be sampled at visit 5-6.
- Working ability (i.e. sick leave, sick pension) will be registered at each visit (NOKLUS study form).
- Cognitive test administration using Memoro, a web-based cognitive test platform developed by [name] and [name], NTNU (28-30). The test can be run on a computer, tablet, or smartphone. Participants receive links via sms, e-mail, as a printed pdf (letter) or through helsenorge.no. Memoro uses same encryption as online banking (nettbanken) and has ROS analysis approving the system. The server is located at NTNU's central server location. No clinical data is stored only the test scores. Some background variables are stored to provide norm data for references (year born, education level according to groups (vgs., bachelor, master or above) and handedness). Participants can receive their scores relative to the norm data if that is of interest. Score will be transferred directly to TSD or similar server at UiT/Haukeland or via encrypted file sender. The cognitive tests that will be used have been used in many other studies (incl. HUNT and MoBa) and have therefore system norms as a reference.

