# CONFIDENTIAL The CORTAD study Clinical Trial Protocol version6.2, 15thNovember 2023

Procedure	ng ation			Intervention Period				
	Screening	Randomization	Baseline	Phone visit	Lab visit			
Visit number	1		2	3	4	5	6	7
Diagnostic laboratory tests adrenal insufficiency 	X							
Laboratory tests (hematology, electrolytes, creatine, liver enzymes, cholesterols and triglycerides, HbA1c, cobalamine, , ferritin, renin, aldosterone, 25OH vitamin D, TSH, FT4)			X			X	X	
HOMA index (insulin and glucose)			X			X	X	
Serum and EDTA samples for Biobanking forc- peptide, bone markers, BDNF, metylmalomic acid and autoantibody screening (etiology and autoimmune comorbidity)			X			X	X	
Urine sample (steroid metabolome)							X	
Hair sample (cortisol)			X				X	
HRQoL questionnaires (RAND-36, AddiQoL-30)			X		X	X	X	
Cognitive tests	X					X	X	
Bone mineral density and body composition					X		X	
Blood sampling 1 and 4 h after morning dose (S-cortisol)					X			
Dose adjustment according to S-cortisol (if applicable) 					X			
Saliva cortisol (before, +1h and +4 h after morning dose						X	X	

© 2015-2021 TransCelerate BioPharma

Doc. No. CT 2.01.01. Valid from 31 Jan 2022.

Only the electronic version is valid.

Page 12 of 65

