# 3. Objectives, Endpoints, and Estimands

The hypothesis to be tested is superiority of Plenadren compared to thrice daily Cortisone to improve patient outcome, including:

- Improved HRQoL, including mood and cognitive function
- Improved sleep quality
- Improved working ability (i.e. less sick leave, lower frequency of sick pension)
- Improved cognitive function
- Reduction in clinical risk factors of cardiovascular and metabolic diseases including weight, waist circumference, blood pressure, lipid profile, bone health, fat distribution and glucose levels.

**Objective**: To determine whether Plenadren or conventional Cortisone is superior for improving overall patient outcome in newly-diagnosed patients with PAI.

**Primary endpoint**: Differences in health-related quality of life (HRQoL) scores in patients receiving Plenadren and conventional Cortisone at time of diagnosis and 1, 6, and 12 months after treatment-initiation in newly diagnosed patients with PAI, using two validated questionnaires: one specific for PAI (AddiQoL-30) and one generic (RAND-36).

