### Evaluation of cognitive function:

 Difference in reaction time and working memory in patients receiving Plenadren and conventional Cortisone at baseline and 6-12 months after treatment initiation, specifically targeting reaction time and working memory. Cognitive test administration using Memoro, a web-based cognitive test platform developed by [name] and [name], NTNU (28-30).

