### 6.4. Blinding, Masking

This is an open-label study; potential bias will be reduced by central randomization.

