# 7. Discontinuation of Study Intervention and Participant Discontinuation/Withdrawal

# 7.1. Discontinuation of Study Intervention

Replacement therapy with either Plenadren or Cortisone is needed at all times. If a participant experience side-effects that might be related to ingredients in the tablet or do not obtain sufficient effect, other means of glucocorticoid replacement must be considered at the discretion of the investigator.

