	patients receiving Cortisone at 1, 6 and 12 months after treatment initiation?	Alternative hypothesis: $H_1$ : $P_{Plen0-12} \neq P_{Cort0-12}$ $P_{Plen (0-12)}$ : Increase in cognitive test scores from Baseline to 6 and 12 months in Plenadrentreated patients $P_{Cort(0-12)}$ : Increase in cognitive test scores from Baseline to 6 and 12 months in Cortisontreated patients	scores by linear mixed effect models for repeated measures
2.8	Is there a difference in change of bone markers in patients receiving Plenadren and patients receiving Cortisone 6 and 12 months after treatment initiation	Null hypothesis:  There is no betweengroup difference in changes of bone markers from baseline to 6 and 12 months of treatment	Between group comparison of longitudinal change bone markers by linear mixed effect models for repeated measures
2.9	BMD/Body composition	Null hypothesis:  There is no betweengroup difference in changes of bone mineral density and body composition from baseline to 12 months of treatment	Between group comparison of longitudinal change in bone mineral density and body composition by linear mixed effect models for repeated measures

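### Participants can ask for their normed cognitive scores with no release date, so a 6-month endpoint result can reach an open-label patient before the 12-month tests and HRQoL forms

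*Protocol*

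**What the plan says.** - **Release of scores.** Section 8.2.1 describes the Memoro platform and adds: "Participants can receive their scores relative to the norm data if that is of interest". No date, visit or condition other than interest is attached.
- **Delivery.** The tests are taken remotely: "Participants receive links via sms, e-mail, as a printed pdf (letter) or through helsenorge.no".
- **Status of the scores.** Section 3 lists as a secondary endpoint: "Difference in reaction time and working memory in patients receiving Plenadren and conventional Cortisone at baseline and 6-12 months after treatment initiation". Objective 2.7 in the table of section 9.1 analyses the longitudinal change by mixed model, defined for the test arm as "Increase in cognitive test scores from Baseline to 6 and 12 months in Plenadrentreated patients" and likewise for the Cortisone arm.
- **Timing.** The Schedule of Activities (section 1.3) has three marks for cognitive tests, which read as screening, visit 5 (day 182) and visit 6 (day 365). The HRQoL questionnaires are marked at baseline and visits 4, 5 and 6.
- **Blinding.** Section 6.4: "This is an open-label study; potential bias will be reduced by central randomization". It names no other measure against bias.

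**The concern.** A trial outcome measured partway through follow-up can be shown to the person who will be measured again. That person knows the assigned drug and can credit or blame it for the score. The later measurements most open to influence are the repeat cognitive tests, which depend on effort, and the AddiQoL and RAND-36, which are self-rated and form the primary endpoint.

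Central randomization protects the allocation. It cannot act on what participants learn afterwards. No section calls for recording who received a score or when, so a later analysis could neither describe the exposure nor adjust for it. How results are returned during follow-up is a matter of trial conduct. The protocol already addresses it, permissively, and an analysis plan cannot undo it.

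**Working it through.** The plan gives no figure on this point, so the check is a tracing of the text.

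**Step 1: is release restricted anywhere?** Section 8.2.1 permits it on interest. The Schedule of Activities, section 8 (opening), section 8.1.1 (including the recruiting physician's task list), section 8.1.2 and section 8.1.3 do not mention return of scores, either to schedule it or to delay it.

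**Step 2: which score can carry information about treatment?**

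| Cognitive test | Can its score reflect the assigned drug? | Outcomes measured afterwards |
|---|---|---|
| Screening (day -31 to 0) | No, it precedes any effect of that drug | Not relied on here |
| Visit 5 (day 182) | Yes | Visit 6 cognitive tests, AddiQoL, RAND-36 |
| Visit 6 (day 365) | Yes | None scheduled |

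Only the visit 5 score matters. The window between it and visit 6 is 365 - 182 = 183 days. The 6-month HRQoL forms would be exposed only if the remote test were taken and its score released before the forms were completed, and the protocol does not fix that order.

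The objectives table in section 3 and objective 2.7 also speak of cognitive function at 1 month, where the Schedule of Activities has no test. If such a test were done, its score would be a second post-treatment result that could be seen before later assessments.

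**Step 3: which analyses use the exposed data?** Objective 1.1 (primary: HRQoL change to 6 and 12 months) and objective 2.7 (cognitive change to 6 and 12 months) both use the 12-month values.

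**Step 4: when does this bias the comparison?** For each arm, let p be the share who see the 6-month score before visit 6, and d the mean change this causes in their 12-month outcome. The shift in the 12-month difference between arms is

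p(Plenadren) × d(Plenadren) - p(Cortisone) × d(Cortisone).

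With equal p and equal d the shift is zero. It is non-zero when these products differ, for example because more patients on one drug ask, or because the same score is read differently by a patient who knows which drug is taken. The protocol gives none of the four quantities, so no size can be computed.

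**The case against.** **The strongest reply** is that the sentence sits in a platform description, beside encryption and server location, and permits feedback without planning any. The trial is openly unblinded for stated reasons, and patients already notice their weight and symptoms and are interviewed about the effect of the medication. Feedback is open to both arms and shows only the participant's own standing against norms. Consent pages were not available for this review, and terms for returning results may stand there.

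Much of this stands. Feedback may be rare, and equal uptake and reaction would leave the comparison unbiased. It does not remove the point: the rule as written allows release of an endpoint result during follow-up, and that route of influence is avoidable.

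**A reader might infer more than the documents support:**

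- *That feedback will happen during the trial.* The text only allows it.
- *That screening feedback is equally harmful.* That score says nothing about how the assigned drug is working.
- *That the scores are part of the primary endpoint.* Section 3 does list "Improved HRQoL, including mood and cognitive function", but as a hypothesis. The same list has a separate item for cognitive function, and the primary endpoint is AddiQoL-30 and RAND-36.
- *That a poor score could lead to a change of drug.* Section 7.1 says that for participants who "do not obtain sufficient effect, other means of glucocorticoid replacement must be considered at the discretion of the investigator", but nothing links Memoro scores to that judgement. Sections 4.3 and 6.6 name a symptom history, cortisol levels and clinical questions as inputs to dosing.
- *That interviewing or dosing staff see the scores.* No section gives them access. Section 8.2.1 describes only transfer to a secure server.

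**Conclusion.** The point holds as a worthwhile, low-cost improvement. Section 8.2.1 sets no release time, so an open-label participant can see a 6-month endpoint result before the 12-month cognitive tests and self-rated HRQoL. Bias in the comparison requires uptake or reaction to differ by arm. That is plausible when patients know their drug and choose whether to ask, but the documents do not show it. A figure in AddiQoL points would rest entirely on invented inputs, so none is offered.

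The conclusion assumes that the Schedule of Activities marks are read correctly as screening, visit 5 and visit 6, and that no rule on release stands in material not shown.

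**What to change.** Amend section 8.2.1 to state that individual Memoro scores are released to a participant only after that participant's visit 6 assessments are complete, and that any earlier release is recorded with its date. If the consent information describes the return of results, align it.

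**Cost:** a sentence or two of protocol text, any ethics approval that the amendment needs (section 10.1.1), and an instruction to whoever releases the scores. Participants still receive their results but wait longer: up to about 12 months from baseline for the screening score, and 183 days for the 6-month score. Visits, sample size and analysis are unchanged.

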### 8.2.2. Body measures

Body weight, height and waist circumference should be measured as follows;

- Weight is registered after bladder voiding
- Shoes and coat/jacket should be taken off
- Pockets should be emptied of heavy objects (i.e. keys, coins, etc)

© 2015-2021 TransCelerate BioPharma

Doc. No. CT 2.01.01. Valid from 31 Jan 2022. Only the electronic version is valid.

Page 33 of 65

### 8.2.3. Blood sampling

Table 8.2.3 Laboratory parameters (blood, serum, plasma)			
Hematology	•		
Hemoglobin	
 
Platelet count / thrombocytes
 
		
WBC/leukocytes			
Lipids			

 
Cholesterol
 
	• LDL		
• HDL	
 
Triglycerides
 
		
Clinical chemistry			
• HbA1c	
 
Potassium
 
		

 
Glucose
 
	
 
Sodium
 
		

 
Creatinine
 
	
 
Cobalamin
 
		

 
Ferritin
 
	• P1NP		
	• 25OH Vitamin D		
Hormones			
• TSH (thyroid stimulating hormone)	
 
Aldosterone
 
		
• Free T4	• Renin		

 
TPO antibodies
 
	
 
Insulin
 
		

 
Cortisol
 
	
 
Insulin C-peptide
 
		

 
ACTH
 
	• 21OH antibody		
• DHEAS			

### 8.2.4. Saliva sampling

Saliva day curve for analysis of cortisol and cortisone, sampled at time 0, 1 and 4 hours after morning dose.

### 8.2.5. Urine sampling

Urine will be sampled for 24 h for analysis of urine cortisol and metabolites (LCMSMS) at visit 5 and 6. Sampling will start early morning with an empty bladder and continue collecting to include the first void the next morning. The participant will measure and register the 24 h urine volume and bring a small sample (10 mL) for analysis.

### 8.2.6. Hair sampling

Hair sampling will be performed at visit 6. We will collect scalp hair samples in AAD patients and healthy controls at one time point. The sampling will be done in concordance with the procedure described by Wester and Van Rossum (2015). First, will separate a lock of hair as thick as a pencil at the posterior vertex of the head. Using a scissor, the lock will as close to the scalp as possible. The proximal three cm of hair will be taped to a paper card with a line marking the proximal end of the sample. Hair samples shorter than three centimeters will be excluded from analysis. In patients with thin hair, we will ensure

© 2015-2021 TransCelerate BioPharma

Doc. No. CT 2.01.01. Valid from 31 Jan 2022.

Only the electronic version is valid.

Page 34 of 65

a cosmetically satisfactory result by collecting two hair locks from two parallel positions of the posterior vertex and joining them together on the paper card. We will note information on when the hair was last washed, hair color, if the hair has been dyed the last three months, use of any hair product at the time of sampling, and patient ethnicity. The hair sample cards were stored in an envelope at room temperature until analysis.

Samples will be placed in a glass vial, labelled, and weighed individually. Samples should weigh close to 10 mg, but samples down to 2.5 mg will be included (Noppe et al, 2015). Then, samples will be cut in 1 cm length and washed in 2 ml LC-MS grade isopropanol at room temperature before left to dry for at least two days. Next, we will transfer the samples to a glass tube for mincing. Following this, we will add 1.4 ml methanol and 100  $\mu$ l internal standards before incubation at 25 °C for 18 hours. Subsequently, samples are to be centrifuged at 4500 rpm, 4 °C for 5 minutes. One ml of clear supernatant will be transferred into a new glass tube and placed under a constant stream of nitrogen gas at 50 °C for drying.

Afterwards, we will add 1 ml 2% methanol and vortexed for 1 minute. Next, samples will be cleaned by solid-phase extraction using Oasis HLB 30 µl 96-well extraction plates on a 96-well positive pressure manifold, conditioned with 1 ml of methanol followed by 1 ml Milli-Q. Then, samples will be loaded with 1 ml of resuspended extract, washed with 1 ml 30% LC-grade methanol in Mili-Q, and eluted twice with 300µl methanol. Finally, samples are again placed under a constant stream of nitrogen gas at 50 °C for drying. Before analysis samples will be stored at 4 °C.

© 2015-2021 TransCelerate BioPharma

Doc. No. CT 2.01.01. Valid from 31 Jan 2022.

Only the electronic version is valid.

Page 35 of 65

[figure not shown]

Fig. 1. Standard method for the quantification of hair cortisol concentration.

# 8.2.7. Bone mineral density and Body composition

Dual-energy x-ray absorptiometry (DXA), GE Healthcare Lunar Prodigy densitometer will be used to measure bone mineral density (BMD) in the lumbar spine (LS) L1-L4, total hip and body composition. The scans were analysed using enCORE software version 17 (SP4) (GE Healthcare). No hardware changes were made during the study period. Calibration will be performed daily using a calibration block consisting of tissue-equivalent material with three bone-simulating chambers, as supplied by the manufacturer (1). Standard imaging and positioning protocols will be used to scan the subjects. All scans will be performed by certified densitometry technologists. In vivo short-term coefficients of variation for total body tissue and lean and fat mass are 0.1%, 0.8%, and 2.5% (2). The VAT short-term repeat measurement error coefficient of variation is 9.8% (3).

For measuring android fat, a region of interest (ROI) is defined with the caudal limit at the top of the iliac crest and the cephalic limit at the base of the skull. The height of the android ROI will be automatically set to 20% of the distance from the iliac crest to the base of the skull. Android ROI contains both visceral adipose tissue (VAT) and subcutaneous adipose tissue (SAT). The software estimates the quantity of SAT in the android ROI. VAT was computed by subtracting SAT from the total android fat. The fat

© 2015-2021 TransCelerate BioPharma

Doc. No. CT 2.01.01. Valid from 31 Jan 2022.

Only the electronic version is valid.

Page 36 of 65

mass data from DXA was transformed to volume using a constant correction factor (0.94g/cm3) consistent with the density of adipose tissue (4).

## 8.2.8. Sleep

Evaluation of sleep will be performed for one week in between visit 5 and 6:

**Actiwatch Spectrum** (Philips), a watch-like accelerometer and photodiode sensor placed on the wrist, will continuously provide information about motor activity, sleep (sleep timing and efficiency), and light exposure (white and colored light) during the experimental protocol. Data can be converted to objective sleep parameters (25)

**Sleep radar**: Sleep quality will be assessed by a newly developed Norwegian Sleep Radar based on radio ultra wideband pulse-doppler radar technology enables long-term non-invasive sleep recording (Somnofy, Vital Things AS). The sleep algorithm has been validated to provide sleep stage classification with a precision close to what can be achieved using brain activity monitoring using deep neural networks machine learning (26).

**Sleep diary**: SurveyXact will be used in consultation with sleep researchers in University of Bergen.

## 8.3. Safety Assessments

Planned time points for all safety assessments are provided in the SoA.

#### 8.3.1. Vital Signs

Pulse rate, pulse quality and blood pressure will be recorded, both sitting and standing, with a completely automated device. Manual techniques will be used only if an automated device is not available.

- Blood pressure and pulse measurements should be preceded by at least five minutes of rest for the participant in a quiet setting without distractions (e.g. television, cell phones).
- For blood pressure measurements, two consecutive blood pressure readings will be recorded at intervals of at least one minute. The lowest of the two blood pressure readings will be recorded. After one minute standing a measurement will be performed.

## 8.3.2. Electrocardiograms

Not applicable.

#### **8.3.3.** Clinical Safety Laboratory Tests

• See the SoA (Section 1.3) for the timing and frequency of laboratory tests.

© 2015-2021 TransCelerate BioPharma

Doc. No. CT 2.01.01. Valid from 31 Jan 2022.

Only the electronic version is valid.

Page 37 of 65

• To assess dose safety, serum cortisol will be measured 1 and 4 hours after the participant has administered the morning dose between visit 2 and 3. If a dose increase or decrease is deemed necessary, cortisol measurement 1 and 4 hours after the participant has administered the morning dose will be repeated after one week.

Table 8.3.3. Laboratory parameters for PAI diagnosis at screening (blood, serum, plasma)			
Hematology			
Hemoglobin	Platelet count / thrombocytes		
WBC/leukocytes			
Lipids			
Cholesterol	• LDL		
• HDL			
	
 
Triglycerides
 
		
Clinical chemistry			
• HbA1c	
 
Potassium
 
		
• Glucose	
 
Sodium
 
		
Creatinine	
 
Calcium
 
		
Ferritin	
 
Albumin
 
		
	
 
Cobalamin
 
		
Hormones			
TSH (thyroid stimulating hormone)	• Renin		
• Free T4	
 
Aldosterone
 
		
	
 
Cortisol
 
		
TPO antibodies	• ACTH		
	
 
DHEAS
 
		
• 21-OH antibodies			

- The investigator must review the laboratory results, document this review, and record any clinically significant changes occurring during the study as an AE. The laboratory results must be retained with source documents.
- Abnormal laboratory findings associated with the underlying disease are not considered clinically significant unless judged by the investigator to be more severe than expected for the participant's condition.
- All laboratory tests with values considered clinically significantly abnormal during
  participation in the study should be repeated until the values return to normal or baseline
  or are no longer considered clinically significant by the investigator or medical monitor.

© 2015-2021 TransCelerate BioPharma

Doc. No. CT 2.01.01. Valid from 31 Jan 2022.

Only the electronic version is valid.

Page 38 of 65

- [If clinically significant/any] values do not return to normal/baseline within a period of time judged reasonable by the investigator, the etiology should be identified, and the sponsor notified.
- All protocol-required laboratory tests must be conducted in accordance with the laboratory manual and the SoA (Section 1.3).
- If laboratory values from non-protocol-specified laboratory tests performed at the institution's local laboratory require a change in participant management or are considered clinically significant by the investigator (e.g., SAE or AE or dose modification), then the results must be recorded.

